1.3 EXPLORATORY OBJECTIVES

1.3.1 To assess the expression of CEA and MUC-1 antigens in bladder tumor specimens pre- and post-treatment in both arms
1.3.2 To assess the presence of CD4 and CD8 T cells in bladder tumor specimens pre- and post-treatment in both arms
1.3.3 To assess the presence of Tregs by double staining with FoxP3 and CD4 in bladder tumor specimens pre- and post-treatment in both arms
1.3.4 To assess the presence of myeloid derived suppressor cells (MDSC) in bladder tumor specimens pre- and post-treatment in both arms
1.3.5 To measure the CD4 antigen-specific response to CEA in peripheral blood mononuclear cells (PBMCs) obtained from blood
1.3.6 To measure the CD8 antigen-specific response to CEA, MUC-1, and Brachyury in all subjects who have the HLA-A2 allele in PBMCs obtained from blood
1.3.7 To analyze all PBMC samples by flow cytometry for the following cell types: CD4, CD8, Tregs, MDSCs, and Natural Killer (NK) cells
1.3.8 To analyze sera samples obtained from blood at all time points for antibodies to CEA, MUC-1, and Brachyury

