10.1.7.1 Biopsies

Biopsies will be obtained at the end of therapy solely for diagnostic purposes as per standard of care to ensure that cancer is no longer present. After pathologic diagnosis, each biopsy specimen will be further analyzed by immunohistochemistry for the following: (a) expression of CEA and MUC-1 antigens on tumor cells, (b) the presence of CD4 and CD8 T cells, (c) the presence of regulatory T cells (Tregs) by double staining with FoxP3 and CD4, and (d) the presence of myeloid derived suppressor cells (MDSC).

Satisfactory analytical performance characteristics (specificity, sensitivity and reproducibility at the minimum) of individual antibodies or affinity ligands for use in immunohistochemistry will be demonstrated prior to analyses of glycosylated CEA and MUC-1 on tumor cells, CD4 and CD8 T cells, Tregs by double staining with FoxP3 and CD4, and MDSC.

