Patient accrual is targeted at one patient per month during the first 6 months and 2 patients per month afterwards, and follow-up period after completing accrual will be 12 months. The power calculation was based on one-sided log-rank test at 15% significance level. Sample size, power and duration of the study are presented in the table below. With a total number of 49 patients, the power is 84% (see table below). Under this scenario, the expected number of events (recurrence or death) is 40. In order to allow for the possibility of a small number of unevaluable patients, the accrual ceiling will be set at 54 patients.

	Subgroup 1 1-year recurrence-free survival for BCG persistent patients who failed 1 BCG induction course	Subgroup 2 1-year recurrence-free survival for BCG persistent patients who failed 2 or more BCG induction courses	Subgroup 3 1-year recurrence-free survival for BCG naïve patients	Total sample size	Power (%)	Duration of accrual (months)	Expected number of events (recurrence or death)
Treatment benefit	HR=2.277 1-year RFS: BCG alone: 37.5% BCG+PANVAC: 65%	HR=2 1-year RFS: BCG alone: 20% BCG+PANVAC: 44.7%	HR=1.7 1-year RFS: BCG alone: 48% BCG+PANVAC: 65%	49	84	28	40

One interim analysis for futility will be performed according to the stopping procedure.³⁹ Specifically, the interim analysis will be performed when half of the expected events (20) have been observed. At that time, if the observed event rate of the TICE BCG+PANVAC arm is higher than that of the TICE BCG alone arm (i.e. the hazard ratio ≥ 1), we would consider terminating the trial and concluding that an advantage for the BCG+PANVAC regimen has not been established.

For the purpose of protecting patient safety, we implement the following stopping rule for safety monitoring of patients who receive the combination therapy.

If one patient experiences a grade 5 event, thought to be possibly or probably due to the combination therapy, the study will be stopped. For grade 3 or 4 event, the study will be stopped according to the following stopping rule. These adverse events are described in more detail in Section 7.

Number of patients	No. of grade 3 or 4 serious adverse events
3-9	3
10-18	4
19-26	5

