14.3 EXPLORATORY/CORRELATIVE ENDPOINTS

14.3.1 To characterize the expression of MUC1 and CEA in bladder tumor specimens pre-(week 0) and the change in expression post-vaccination (on tissue obtained between weeks 17-20) for patients treated with TICE BCG+PANVAC™.

14.3.1.1 MUC1 expression will be evaluated using IHC. A positive result is defined if >5% of tumor cells reacted with any intensity. Intensity will be arbitrarily scored on a 4 point scale: 0 (no staining), 1+ (weak staining), 2+ (moderate staining), and 3+ (strong staining). Potential antibody will be clone Ma695 dilution 1:100 (Novocastra, Newcastle upon Tyne, England) but has to be analytically validated using appropriate positive and negative controls prior to use.²²

14.3.1.2 CEA expression in FFPE pre- and post-treatment tissues will be evaluated by IHC. A positive result is defined when the cytoplasmic staining is equal in intensity to glycocalyceal staining. Tumors will be scored as 0 (no signal), 1+ (signal in <25% sampled tumor area), 2+ (26-75% of tumor cells), and 3+ (>75% of tumor cells). The potential antibody will be CD66e (clone 12-140-10; Novocastra, Newcastle upon-Tyne, England; dilution 1:500; Ventana NexES immunostainer; protease digestion).

14.3.1.3 **Statistical Analysis:** For both MUC1 and CEA expression the distributions of IHC staining intensity at baseline and post-vaccination as well as the change in score will be summarized with descriptive statistics. The results will be summarized by calculating the proportion and 95% confidence interval of positive staining tissue samples at baseline and the distribution of pre and post-vaccination combinations (--, -+, +-, ++) characterizing the change with treatment. Results will be presented separately for each treatment arm. The distributions for the two treatment arms will be compared using a chi square test.

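### The between-arm chi-square on pre/post MUC1 and CEA categories can use only patients with tumour at weeks 17-20, so it is conditioned on an outcome that randomisation does not balance and is too sparse for the approximation

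*Combined protocol and SAP*

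**What the plan says.** The first exploratory objective in section 1.3 is: "To assess the expression of CEA and MUC-1 antigens in bladder tumor specimens pre- and post-treatment in both arms". Section 14.3.1.3 summarises each marker by its baseline positivity and by "the distribution of pre and post-vaccination combinations (--, -+, +-, ++) characterizing the change with treatment", separately for each arm. It then adds: "The distributions for the two treatment arms will be compared using a chi square test".

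Both markers are read on tumour. Section 14.3.1.1 calls MUC1 positive when more than 5% of tumour cells stain. Section 14.3.1.2 grades CEA by the share of tumour area or tumour cells with signal. Section 10.1.7.1 likewise places both antigens on tumour cells.

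The post-treatment tissue is the week 17-20 specimen. Section 10.1.7.1 says that end-of-therapy biopsies are taken "solely for diagnostic purposes as per standard of care to ensure that cancer is no longer present". Section 5.2.2.3, written for the BCG arm, says that a patient with recurrent tumour at that look has reached the primary endpoint. Section 12.1.1.3 defines recurrence by pathological confirmation in both arms.

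The plan gives no rule for patients without tumour at weeks 17-20, no expected number of scorable pairs and no small-sample alternative for this table. Elsewhere it does use Fisher's exact test: for toxicity grades (14.2) and for CD8 response (14.3.3.2).

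**The concern.** A patient who is disease-free at weeks 17-20 has no tumour cells to score and fits none of the four categories. Only treatment failures enter the table, and the trial's hypothesis is that failure is less frequent on BCG+PANVAC. The two groups compared are therefore not the randomised groups. A difference between them, or the absence of one, may reflect who is left with tumour rather than what treatment did to expression. No choice of test removes that.

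Separately, a handful of patients spread over eight cells is far below what the chi-square approximation needs. At stake is the interpretation of one exploratory correlate: the table is described as characterising change with treatment, and a between-arm p-value invites a causal reading that it cannot carry.

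**Working it through.** **1. Inputs.** From section 14.1: 49 patients, with a ceiling of 54; subgroup mix 1:5:1; exponential recurrence-free survival; one-year rates on BCG alone versus BCG+PANVAC of 37.5% v 65%, 20% v 44.7% and 48% v 65%. From section 4.3: equal allocation, so 24.5 per arm. From section 12.1.1.3: time runs from BCG start at week 3, so weeks 17-20 are 14 to 17 weeks after the origin. From section 2: MUC1 in 93% of bladder tumours; CEA in 76% of high-grade and 59% of pT1 tumours.

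**2. The plan's own figures.** Hazard ratios ln(S_control)/ln(S_experimental) are 2.277, 2.00 and 1.70, as stated. The plan says "the expected number of events (recurrence or death) is 40". Simulating its accrual and follow-up gives 40.0 events and power of 0.86 (stated 84%) for the one-sided 15% log-rank test. The inputs therefore reproduce the plan. It states no figure for the MUC1/CEA comparison.

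**3. Scorable patients.** The proportion with an event by week t after BCG start is the sum over subgroups of weight x (1 - S^(t/52)), where S is the one-year rate. At the midpoint, t = 15.5:
- BCG alone: (0.2535 + 5 x 0.3811 + 0.1965)/7 = 0.336; x 24.5 = 8.2
- BCG+PANVAC: (0.1205 + 5 x 0.2133 + 0.1205)/7 = 0.187; x 24.5 = 4.6

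| Look (weeks after BCG start) | BCG alone | BCG+PANVAC | Total, N=49 | Total, N=54 |
|---|---|---|---|---|
| 14 | 31.0%, 7.6 | 17.0%, 4.2 | 11.8 | 13.0 |
| 15.5 | 33.6%, 8.2 | 18.7%, 4.6 | 12.8 | 14.1 |
| 17 | 36.2%, 8.9 | 20.3%, 5.0 | 13.8 | 15.2 |
| All 12-month events already present | 73.5%, 18.0 | 49.5%, 12.1 | 30.1 | 33.2 |

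The counts beside the percentages are for N=49. The last row is a deliberate upper bound.

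**4. Sparsity.** For all eight cells to have an expected count of 5, the table needs at least 8 x 5 = 40 patients. Thirteen patients average 13/8 = 1.6 per cell. With 8 versus 5 patients, 7 or 8 of the 8 expected counts are below 5 for every distribution tried.

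**5. True size of the nominal 5% chi-square at 8 versus 5.** Full enumeration of the tables under no arm difference. Assumption: pre and post status independent, with post positivity equal to pre or 20 points lower.

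| Positivity pre/post | 3 df | Empty columns dropped |
|---|---|---|
| 93%/93% | 0.06% | 0.8% |
| 93%/73% | 0.4% | 2.7% |
| 76%/76% | 1.1% | 2.9% |
| 76%/56% | 1.8% | 3.2% |
| 59%/59% | 2.6% | 3.2% |
| 59%/39% | 2.5% | 3.2% |
| Four equal categories | 2.8% | 3.3% |

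The lower end depends on the distribution assumed. The direction does not: the test under-rejects throughout.

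**6. What selection would do to the table.** Assume CEA positivity of 76%, no change in any tumour's expression, and a vaccine benefit confined to antigen-positive tumours. Antigen-negative tumours are then 24% of failures on BCG alone, but 0.24 x 0.336/0.187 = 43% of failures on BCG+PANVAC. Each patient is classified by their own two readings, so this moves share from `++` to `--` and puts nobody in `+-`.

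**The case against.** The strongest reply has four parts.

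First, the table is paired. A reader might infer that selective clearance of antigen-positive tumours would masquerade as vaccine-induced antigen loss. The documents do not support that: with unchanged expression, an antigen-negative failure falls in `--`, while loss is `+-`. This stands. What remains is that the arms' distributions can differ with no effect on expression, and the chi-square tests all four categories together. With MUC1 at 93% there is also little room for baseline selection on that marker.

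Second, the figure of about 13 is derived, not stated. It carries a constant hazard back to the first scheduled post-treatment biopsy, in a population where 5/7 are expected to have persistent disease after two or more courses. Persistent disease could surface at that look and raise the number. Deaths counted as events, and tissue collected only if available (5.1.3, 10.1.4), would lower it. This stands as a caveat, hence the bound of about 30. At 18 versus 12 the chi-square's size was 3.0-4.8% in simulation (empty columns dropped), so strong conservatism depends on the low count. Even at 19 versus 13, 5 to 7 of the 8 expected counts are below 5.

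Third, a reader might infer that an invalid approximation means excess false positives. The calculations show the opposite. An exact test changes little, with a size of about 0.8-3.6% over the same distributions at 8 versus 5. It addresses only the approximation.

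Fourth, a tempting repair is to compare all randomised patients on no tumour, antigen-positive tumour or antigen-negative tumour. That mostly re-tests recurrence. With identical antigen distributions in both arms and planned recurrence of 34% versus 19%, the Fisher-Freeman-Halton test at 25 versus 24 patients rejects 15-16% of the time at 0.05. It also discards baseline status.

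**Conclusion.** The point holds as a minor one. The between-arm chi-square in 14.3.1.3 is confined to patients who have already met the primary endpoint. Under the planning rates these are about 34% of BCG-alone patients and 19% of BCG+PANVAC patients at the middle of the biopsy window. That is 12-14 of 49 in total, and at most about 30. Randomisation does not protect the comparison, and the table stays below the 40 patients needed for adequate expected counts even at the bound, or at 33 with the ceiling of 54. At the likely size the p-value is conservative and the test has almost no power.

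The restriction to tumour-bearing patients follows directly from the scoring rules. The counts rest on exponential survival and the plan's subgroup rates, and the size figures rest on the category distributions assumed above. Baseline positivity is unaffected, because entry requires histologically confirmed tumour (3.1.1.1).

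A reader might also extend the criticism to the CD4, CD8, Treg and MDSC tumour infiltrates. The documents do not support that: section 14.3 specifies no between-arm test of infiltrates, its CD4 and CD8 analyses use blood cells, and section 10.1.7.1 limits only CEA and MUC1 to tumour cells.

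**What to change.** In 14.3.1.3, replace the sentence on the between-arm chi-square with the following provisions:
- Present the four-way pre/post table for each marker by arm, descriptively, among patients with scorable post-treatment tumour.
- Report, as separate rows for each arm, the number with no tumour at weeks 17-20 and the number with missing tissue.
- State that differences between arms in this table are not to be read as a treatment effect on expression, because inclusion depends on recurrence.
- If a p-value is kept, use the Fisher-Freeman-Halton exact test and label it as conditional on recurrence. This matches the plan's use of exact tests in 14.2 and 14.3.3.2.

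Do not substitute a three-level test on all randomised patients.

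The cost is a few sentences, with the same samples and assays. What is lost is one exploratory p-value with almost no power.

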14.3.2 To explore the CD4 Antigen-Specific response to MUC1 and CEA

14.3.2.1 The CD4 antigen-specific response will be assessed by culturing CD4+ T cells obtained from PBMCs pre- and post-treatment with irradiated APCs in the presence of MUC1 and CEA peptides/proteins. The IFN- γ levels will be measured by ELISA. Flu protein (positive control) and myoglobin (negative control) will serve as controls.

14.3.2.2 **Statistical Analysis:** Descriptive statistics will be calculated to summarize the CD4 antigen-specific response to MUC1 and CEA determined pre-treatment as well as the change post-vaccination. The same methods for analysis for each treatment arm and the comparison of arms as described for evaluation of the immune response to the vaccines will be applied.

14.3.3 To explore the CD8-mediated immune response to MUC1 and CEA

14.3.3.1 Assess CD8 T cell response by ELISPOT assay in pre- and post-treatment PBMCs using CEA and MUC1-specific T lymphocytes. We will be using an overlapping peptide library that will allow for the ability to test ~65% of HLA groups for MUC1 and ~80% of HLA groups for CEA

14.3.3.2 **Statistical Analysis:** A positive CD8 T cell response is defined as ≥ 2 -fold increase post treatment compared with the pretreatment value in IFN- γ -secretion. Descriptive statistics will be calculated to summarize the CD8 T cell response as continuous variables to MUC1 and CEA at both time points for each study arm. In addition, the change from pre- to post-treatment will be summarized by the proportion of patients achieving a positive response. The proportion with 95% confidence intervals will be presented for each treatment arm along with additional descriptive statistics (e.g. mean change, the mean percent change). Fisher's exact test will be performed to compare the positive CD8 T cell response between the two treatment arms.

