10.1.5 Collection of immunologic blood samples

For the BCG alone arm:

- at week 0 or at randomization by 1 10cc purple top tube
- prior to treatment at weeks 3 and 8 by 2 10cc red top tubes and 6 10cc green top tubes
- at the end of study (between weeks 17-20) by 1 10cc purple top tube, 2 10cc red top tubes and 6 10cc green top tubes.

For the BCG + PANVAC vaccine arm:

- at week 0 by 1 10cc purple top tube

- prior to treatment at weeks 0, 3, 8, 11, and 15 by 2 10cc red top tubes and 6 10cc green top tubes
- at the end of study (between weeks 17-20) by 1 10cc purple top tube, 2 10cc red top tubes and 6 10cc green top tubes.

Additionally, blood may be collected on follow-up visits for up to 12 months following end of study cystoscopy/ bladder biopsy. From this blood, PBMCs and sera will be isolated, when appropriate samples are available, for the following immune correlates:

Immunologic testing will include:

1. Circulating Tumor Cytokines (CTC) analysis
2. IFN-gamma ELISPOT assays for CD8 T-cell responses specific for CEA, MUC-1, and Brachyury (Limited to patients with HLA-A2 allele)
3. Measure CD4 antigen-specific response to CEA
4. Sera samples will be analyzed for the development of antibodies to CEA, MUC-1 and Brachyury. (Samples from baseline and at end of study)
5. Flow cytometry analysis using 10 markers of all PBMC samples for each of the following cell types: CD4, CD8, Tregs, MDSCs, and NK.
6. Serum for NCA (CEA-CAM) titers will be drawn anytime that a patient exhibits new onset neutropenia (ANC <1000)
7. Immunologic studies will be repeated more frequently if clinically indicated, and any abnormalities potentially related to treatment will be followed until they have resolved, or have been determined to not be treatment-related or until the participant's primary medical care is transferred from the principal investigator.

10.1.6 The immunologic testing samples for CTC analysis will be processed at:

[name] Lab
[name]
[name]

For patients at CINJ, research samples consisting of 2 purple top tubes (week 0 and week 17-20) will be drawn. These tubes will be further processed as per Appendix E, Section **17.5** and then shipped via Fed-Ex to [name] lab:

[name]
c/o [name] or [name]
Urologic Oncology Branch
[name]
[name]

10.1.7 The other immunologic testing samples will be processed at:

Clinical Services Program
NCI Frederick Cancer Research and Development Center
[name]

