10.1.7.2 PBMCs, sera, and urine

The following time points will be analyzed: baseline (prior to vaccination in vaccination arm), week 3 (prior to BCG for both arms), week 8 (prior to last BCG for both arms), and at end of study (between weeks 17-20).

PBMCs

All patients who have the HLA-A2 allele will be analyzed by ELISPOT for CD8 T-cell responses specific for CEA, MUC-1, and a cascade antigen Brachyury. All samples will be evaluated for CD4 responses specific for CEA protein. All immune assays will have appropriate antigen controls. All PBMC samples will be analyzed by flow cytometry using 10 markers for each of the following cell types: CD4, CD8, Tregs, MDSCs, and NK.

- Satisfactory analytical performance characteristics of individual antibodies or affinity ligands for use in ELISPOT, flow cytometry, or ELISA will be demonstrated prior to analyses of the proposed protein markers, cytokines and chemokines.
- Analyses of sera samples for quantitation of antibodies to CEA, MUC-1 and a cascade antigen Brachyury will be described in detail to show clinically recapitulated tumor-associated antigens, including glycosylated proteins, are used in measuring autoantibodies in sera.

Background: Our studies in the LTIB have demonstrated the ELISPOT assay for IFN- γ production to be quantitative and reproducible as a measure of human T-cell responses to vaccination (26). The continued use of one reproducible assay has been instrumental in our ability to evaluate and compare patients' immune responses using different vaccines and vaccine strategies in the same institution, and among different cancer centers. ELISPOT assays employing the CEA agonist peptide and the MUC-1 agonist peptide have already been developed.

Sera

Sera samples at all time points will be analyzed for the development of antibodies to CEA, MUC-1, and a cascade antigen Brachyury.

Urine

Urine samples may be collected at baseline and at the end of therapy (week 17-20) for the presence of cytokines and chemokines. In addition, an effort will be made to collect urine at the time of BCG instillation #1 and #3 to assess for cytokine production in response to BCG therapy (as described earlier in section **10.1.2** and in Section **17.5** (Appendix E)).

For patients at CINJ, research samples consisting of urine (week 0, week 3, week 5, and week 17-20) will be drawn. These tubes will be further processed as per Appendix E, Section **17.5** and then shipped via Fed-Ex to [name] lab:

[name]

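### The CD8 responder rule in 14.3.3.2 is a bare 2-fold rise with no absolute minimum, no zero-baseline rule and no use of the control wells, so at low spot counts it can count unchanged patients as responders

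*Combined protocol and SAP*

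**What the plan says.** Section 14.3.3.2 defines a positive CD8 response by the ratio alone: at least a "2 -fold increase post treatment compared with the pretreatment value" in IFN-gamma secretion. Responder proportions with 95% confidence intervals are reported by arm, and a Fisher "exact test will be performed to compare the positive CD8 T cell response between the two treatment arms". Mean change and mean percent change are also planned. One analysis avoids the cut-off: "Descriptive statistics will be calculated to summarize the CD8 T cell response as continuous variables to MUC1 and CEA at both time points".

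On assay quality, 10.1.7.2 states that "All immune assays will have appropriate antigen controls" and describes the IFN-gamma ELISPOT assay as having been shown for IFN-gamma "production to be quantitative and reproducible as a measure of human T-cell responses to vaccination". It also requires satisfactory analytical performance to be shown before the analyses. A negative control is named only for the CD4 assay, in 14.3.2.1: "Flu protein (positive control) and myoglobin (negative control) will serve as controls". Nothing links any control to the CD8 responder rule.

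On who is tested, 10.1.5 says "Limited to patients with HLA-A2 allele", whereas 14.3.3.1 describes a peptide library that covers about 65% of HLA groups for MUC1 and about 80% for CEA.

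**The concern.** A pure ratio takes no account of the size of the counts behind it. A move from 1 spot to 2 meets the rule as fully as a move from 50 to 100, although the first is well within counting error. If the baseline is zero the ratio does not exist, and neither does the planned percent change. Someone would then have to decide those cases after seeing the data, in an open-label trial.

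The background section bases the trial on a vaccine-augmented cytotoxic T-cell response, and this Fisher test is the only between-arm test specified for the CD8 response. If noise makes responders in both arms, the proportions and their intervals partly describe the assay, and the arm difference shrinks.

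**Working it through.** The plan states no false-positive rate, power or sample size for this endpoint, so there is no figure to reproduce.

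**Inputs.** From the plan: the 2-fold rule, Fisher's exact test, equal allocation and 49 patients in total. Not in the plan, and therefore assumed over a range: spot counts, background, assay CV, true response rates, number tested, and the level and sidedness of the Fisher test.

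**1. No true change, counting error only.** Let the pre count X and post count Y be independent Poisson with the same mean m. A zero baseline followed by any positive count is taken as a rise; 0 to 0 is not. The false-responder rate is f = P(Y ≥ 2X and Y > 0). At m = 1, zero baselines contribute 0.368 × 0.632 = 0.233 and non-zero baselines 0.101, which gives 0.333.

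| Mean spots | P(baseline = 0) | f, bare rule | f from non-zero baselines | f, also a rise ≥ 10 |
|---|---|---|---|---|
| 1 | 36.8% | 33% | 10% | <0.1% |
| 2 | 13.5% | 32% | 20% | <0.1% |
| 3 | 5.0% | 27% | 22% | <0.1% |
| 5 | 0.7% | 18% | 18% | 0.2% |
| 10 | <0.1% | 8.4% | 8.4% | 1.7% |
| 20 | <0.1% | 2.2% | 2.2% | 2.1% |
| 30 | <0.1% | 0.6% | 0.6% | 0.6% |

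**2. Assay variability.** With lognormal error alone, f = 1 − Φ(ln 2 / (√2 σ)) and σ² = ln(1 + CV²). At CV 40%, σ = 0.385, the argument is 0.693 / 0.545 = 1.27, and f = 10%. At CV 20%, 30% and 50%, f is 0.7%, about 5% and 15%. With Poisson counts plus 30% extra CV (simulated), f is 16% at mean 10, 11% at mean 20 and 7% at mean 50. Adding a 10-spot floor leaves about 6%, 10% and 7%, so a fixed floor is not a full remedy in a noisy assay.

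**3. Background, stable over time.** Let b background spots be added to both counts.
- Constant true signal of 2 spots, background left in: f is 32% at b = 0, 13% at b = 5 and 1.7% at b = 20. Subtracting background without a floor keeps f near 34%.
- True rise from 5 to 15 spots, background left in: the observed ratio is (15 + b)/(5 + b), which is 3.0, 1.67 and 1.4 at b = 0, 10 and 20. The rise is called positive 83%, 32% and 10% of the time.

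Stable background therefore causes missed responders, not extra ones.

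**4. Background that rises after treatment.** Constant true signal of 2 spots, background going from 5 to 10 or from 5 to 15:
- bare rule: 42% and 71%;
- 10-spot floor without subtraction: 15% and 53%;
- subtraction plus the floor, with the net pre value set to at least 1: about 2% and 4%.

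**5. Effect on the Fisher test.** If a fraction f of true non-responders is miscalled in each arm, a true rate p is observed as p + (1 − p)f, so the arm difference shrinks by the factor (1 − f). Take true induction of 50% vs 0%, two-sided 0.05. If about half of 49 patients are tested, there are about 12 per arm.

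| f | Observed rates | Power, 12 per arm | Power, 20 per arm |
|---|---|---|---|
| 2% | 51% vs 2% | 73% | 97% |
| 15% | 57.5% vs 15% | 45% | 75% |
| 30% | 65% vs 30% | 29% | 47% |

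**The case against.** The strongest reply is that the documents do not place the assay in the range where the rule fails. They give no spot counts, background, CV or detection limit. The description of tumor antigens as weakly immunogenic is a reason for using poxviral vectors; it is not a statement about ELISPOT counts. At 20 spots or more with low CV the bare rule is harmless. This stands, and it makes the size conditional. It does not supply the missing rules, and a definition that works only at adequate counts should state its minimum.

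A second reply is that the endpoint is one of nine exploratory objectives, carries no alpha or power, and has continuous summaries beside it. That also stands and sets the severity. The Fisher figures rest on assumed response rates and an assumed number tested, and 10.1.5 and 14.3.3.1 leave that number unsettled.

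A reader might also infer some stronger points that the documents do not support:
- **Missing background subtraction inflates responders.** Under stable background the effect is the reverse (step 3). It inflates them only if background itself rises after treatment. BCG could do that, but the documents do not show it.
- **A change from 0 to 0 spots counts as positive.** That would give 47% at mean 1 and 34% at mean 2, but the rule requires an increase.
- **Response to either CEA or MUC1 counts.** At 30% per antigen and with independence this gives 1 − 0.7² = 51%, but 14.3.3.2 states no such composite.

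**Conclusion.** The gap is real and minor. The rule in 14.3.3.2 lacks an absolute minimum, a zero-baseline rule and any stated use of the controls. With no true change and Poisson counts, it labels about 8% to 33% of patients as responders at means of 1 to 10 spots and about 2% or less at 20 or more, with higher rates if assay CV is substantial (10% at CV 40% under lognormal error). The missing minimum causes these false responders; the missing subtraction is a separate fault that mainly hides true ones. Both weaken the Fisher comparison: in the illustrative case of 50% vs 0% with 12 tested per arm, power is 73% with 2% false responders and 45% with 15%.

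It would go too far to say that patients in this trial will often be misclassified, because that depends on counts and a CV that the documents do not give. The effect is confined to the CD8 responder proportions, their confidence intervals and the Fisher test. The primary analysis and the sample size are untouched.

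**What to change.** In 14.3.3.2:
- Subtract the matched negative-control wells at each time point, and name the control for the CD8 ELISPOT.
- Call a response positive only if the background-subtracted value rises at least 2-fold **and** the absolute rise exceeds a prespecified minimum. Take that minimum from the assay's own repeatability data; the 10 spots used above is only an illustration. The two conditions belong together, since subtraction without a floor leaves false responders near 34% in the example.
- Set pre values at or below the detection limit to that limit before forming the ratio or the percent change.
- Define response per antigen.
- Keep the bare 2-fold rule as a sensitivity analysis.

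The cost is wording only, using controls already planned. The downside is that reported responder rates will be lower and a few small true rises will be missed.

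### The only between-arm CD8 comparison is Fisher's exact test on a fold change cut at 2, which can cost substantial power against a test on the continuous values already collected

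*Combined protocol and SAP*

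**What the plan says.** Section 14.3.3.2 sets the cut: "A positive CD8 T cell response is defined as ≥ 2 -fold increase post treatment", relative to the pretreatment IFN-gamma value. It treats the same measurement as continuous for description: "Descriptive statistics will be calculated to summarize the CD8 T cell response as continuous variables to MUC1 and CEA at both time points", by arm, with "additional descriptive statistics (e.g. mean change, the mean percent change"). Responder proportions get 95% confidence intervals within each arm. Between arms there is one procedure, Fisher's "exact test will be performed to compare the positive CD8 T cell response between the two treatment arms".

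Section 10.1.7.2 describes the "ELISPOT assay for IFN- γ production to be quantitative and reproducible as a measure of human T-cell responses to vaccination".

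The analysis sits under "EXPLORATORY/CORRELATIVE ENDPOINTS" (Section 14.3). No alpha, power or assumed effect is attached to it. The only power statement in the plan concerns the primary endpoint (Section 14.1): "With a total number of 49 patients, the power is 84% (see table below").

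**The concern.** A 1.9-fold rise is tested as if nothing had happened, and a 20-fold rise counts the same as a 2-fold one. Fisher's test is also conservative at this sample size. The continuous values are summarised within each arm, but no between-arm estimate or test uses them.

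The Background (Section 2) hypothesises a stronger immune response with PANVAC plus BCG than with BCG alone, and this comparison bears directly on that hypothesis. With one or two dozen evaluable patients per arm, the planned test may miss a difference that the same samples could show.

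**Working it through.** **The plan's own figure.** There is none for CD8. The primary-endpoint figure that fixes N can be reproduced. The hazard ratios follow from ln(S_BCG)/ln(S_combination); for example, ln(0.375)/ln(0.65) = 2.277. Simulating the 1:5:1 mix, the stated accrual and 12 months of follow-up gives 85.5% power and 39.6 events without the interim look, and 82.5% power with the futility look. The plan states 84% and 40.

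**Patients per arm.** Randomisation is equal (Section 4.3), so 49/2 is about 24. The assay restriction is inconsistent:
- Sections 1.3.6, 10.1.5 and 10.1.7.2 limit CD8 ELISPOT to HLA-A2 carriers. Their prevalence is not given. If half carry it (assumed), 0.5 × 24.5 is about 12.
- Section 14.3.3.1 describes a peptide library covering about 65% (MUC1) and 80% (CEA) of HLA groups. Read as shares of patients, that is about 16 and 20.

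The check therefore uses n = 12 and n = 24 per arm.

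**Assumed inputs.** Two-sided 5% level; responder rates as listed; log2 fold change with cut at log2(2) = 1.

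**Model 1: every vaccinated patient shifts.** Log2 fold change is normal with the same SD in both arms.
- Standardised shift: d = Φ⁻¹(p1) − Φ⁻¹(p0). For 20% v 50%, d = 0 + 0.842 = 0.842.
- t-test power: noncentral t, df = 2n − 2, noncentrality d√(n/2). At n = 12 this is 0.842 × √6 = 2.06; at n = 24, 0.842 × √12 = 2.92.
- Fisher power: the product of the two binomial probabilities, summed over all tables with p ≤ 0.05.

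| Responders, BCG v combination | n per arm | Fisher | t test | Loss (points) |
|---|---|---|---|---|
| 20% v 50% | 12 | 21% | 50% | 29 |
| 20% v 50% | 24 | 49% | 81% | 32 |
| 20% v 60% | 12 | 39% | 73% | 34 |
| 20% v 60% | 24 | 76% | 96% | 20 |
| 10% v 40% | 12 | 23% | 67% | 44 |
| 10% v 40% | 24 | 60% | 94% | 34 |

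Part of the loss is Fisher's conservatism. With equal true response rates of 10 to 30%, its actual size is 0.2 to 1.7% at n = 12 and 1.7 to 2.6% at n = 24.

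A wider grid (n 8 to 27, shift 0.5 to 1.5 SD, control rate 5 to 31%) gives losses of 2 to 64 points, median 29. The range in the table is central, not a bound.

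**Model 2: only a subset responds.** A share of 30, 50 or 70% of vaccinated patients has log2 fold change N(2.5, SD 0.8). All other patients have mean 0 with SD 0.5 or 0.9. Simulated Welch t against Fisher:
- n = 12: the t test gains about 2 to 20 points. With 30% responding and SD 0.9, Fisher has 14% and t 27%.
- n = 24: the gain is 0 to 14 points. With 30% responding and SD 0.9, Fisher has 41% and t 54%. With 30% responding and SD 0.5, they tie at 75%.
- n = 24, 30% responding, SD reduced to 0.3: Fisher leads, 87% v 85%.

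A separate subset grid with other shifts and noise levels, n = 10 to 24, gives differences from 4 points in Fisher's favour to 32 in favour of the t test. The 32 arises at n = 10.

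**Choice of replacement.** In that grid a Wilcoxon test falls as much as 45 points below Fisher (n = 24, 30% responding, SD 0.3: 44% v 89%). A mean-based test does not carry that risk.

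**The case against.** **The loss depends on the model.** A reader might infer an unconditional loss of 20 to 40 points. The documents do not support that, because they fix none of the inputs. Response in only a subset of vaccinated patients is plausible for an antigen-specific assay, and there the loss is smaller. Nor can one say that the t test is always equal or better, since Fisher is slightly ahead in the low-noise subset cases. This part of the objection stands and sets the limits of the claim.

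**The endpoint is exploratory.** No decision rule, sample size or efficacy conclusion depends on it. This stands and lowers the weight of the point.

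**The continuous data are already reported.** This is true within each arm, so a 20-fold and a 2-fold rise are not hidden from the reader. But no between-arm estimate or interval on that scale is planned, so the objection stands only in part.

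**Log fold change has its own weakness.** With zero or very low pretreatment counts, the added constant matters. In one illustrative count model (many zeros, 30% v 5% responding, n = 24), Welch power moved from 32% to 54% as the constant went from 0.1 to 5. This stands as a condition on the fix. The 2-fold rule has the same gap, because Section 14.3.3.2 does not say how to class a patient with a zero baseline.

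**CD4.** A reader might extend the point to Section 14.3.2.2. That section names neither a 2-fold cut nor Fisher's test; it refers only to methods for evaluating the immune response to the vaccines. No CD4 loss can be claimed.

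**Conclusion.** The point holds in conditional form. The plan's only between-arm CD8 comparison discards the size of a response that the plan measures and summarises as continuous.

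In the scenarios tried with 12 to 24 patients per arm, two-sided 5%, the cost is about 20 to 44 points of power under a roughly normal shift in log fold change. It is about 0 to 20 points if only a subset responds, with a tie or slight reversal when assay noise is low. All effect sizes, SDs, response rates, the alpha and the evaluable numbers are assumed.

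The weight is modest. What is at stake is the information the trial gives on an immune correlate, not its efficacy conclusion. The change is still worth making, because the possible gain is large and the possible loss was at most a few points in the scenarios tried.

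**What to change.** In Section 14.3.3.2, for each of MUC1 and CEA:
- Make the between-arm comparison a Welch t test, or a permutation test on the difference in means, of log2(post/pre) IFN-gamma response. Do not substitute a rank test by default.
- Report the ratio of geometric mean fold changes with its 95% CI.
- Pre-specify the constant added for zero or very low counts, and a sensitivity check with other values.
- Keep the proportion with at least a 2-fold rise, with its 95% CI, as a summary. Fisher's test may stay as supportive.
- State which patients are evaluable, reconciling the HLA-A2 restriction with the peptide-library description.

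The cost is a few sentences of SAP text and no new samples or assays. The remaining drawback is that the result will depend somewhat on the chosen constant, which the sensitivity check would show.
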